
Study staff will send the consent and assent forms to participants via mail or email and allow some time for participants to discuss their participation with family or others before deciding to take part in the study by providing their verbal consent. Study staff obtaining verbal consent will specifically check with potential participants to see if they want to discuss their decision with family members or others before providing their verbal consent.

d. Use of individuals other than the investigators to explain the research

Only the investigators and study staff who are designated to obtain consent will contact the potential participants to explain the research project

e. Types of forms used (e.g., adult consent form, assent form for ages 7-12, parental consent form, youth simplified consent form for ages 13 to 17, foreign language translations)

We will use a parental consent form and assent form for participants ages 16 and 17. We will only use an English adult consent form.
 
The adult and parental consent form, and assent form will be comprehensible to participants by ensuring readability checks on the type of language used, simplicity of language, and additional explanation of concepts.
 
We request for a waiver of documentation of the consent form by the CDU IRB. Due to the COVID-19 pandemic, we will be conducting all research activities remotely. The

research is minimal risk and involves no procedures for which written consent is normally required outside of the research context. The procedures for this study involve demographic surveys, pre- and post- surveys, group and personal discussions. To obtain an effective verbal consent over the phone, we will send the consent form to the potential participants by e-mail or postal mail so that they can review the consent document before the phone call. After we go over every element of the consent, we will do a teach-back and/or Q&A to assess the individual’s understanding of the study. We will ensure that all the individual’s questions about the research have been answered to their satisfaction before they make their decision. The potential participant’s decision to enroll or not enroll into the study will be recorded and logged into their study file along with the date and time.

23. Comprehension of the Information Provided: How will it be determined whether or not the participant or their legally authorized representatives understood the information provided?

We will use a “teach back” method to determine that the participants understood the information in the consent. In particular, we will ensure that the questions in the evaluation to provide verbal consent are clear to the participants by conducting a question-and-answer process as well.

24. Information Withheld from Participants: Will any information about the research purpose and design be withheld from participants? If so, please explain the non-disclosure and describe plans for post-study de-briefing.

No information will be withheld from the participants.

Data Analysis

25. Data Analysis: Please describe the data analysis plans for this study. Include planned statistical analyses and explanation of sample size determination.

Aim 3 - After data cleaning, we will assess psychometric properties of all scaled measures, calculate descriptive statistics to ensure quality of the data (check distributions, examine outliers) and to describe study participants. Bivariate analyses will include independent t-tests models (or their nonparametric equivalents, e.g. Wilcoxon rank-sum test, differences between the groups in trust and self-efficacy. Paired-tests (or Wilcoxon signed-rank test) will be used to assess change within groups. Contingency table analyses will address intention to participate in COVID-19 testing and vaccination. We will then fit multiple regression models predicting change in COVID-19 testing- and vaccine-related knowledge, trust, and self-efficacy as a function of intervention group, racial/ethnic group, and possible interactions. We will use covariate adjustment approaches such as multiple linear and logistic regression models for the three outcomes (trust, self-efficacy, intent to participate) while controlling for demographic characteristics (e.g. age, gender, education, health status) and other potential covariates that will be identified a priori. We do not anticipate many missing data, given the format of completion. However, if we do have 10% or more missing, we will impute data using SAS PROC MI and SAS PROC MIANALYZE to implement these multiple imputation procedures. With respect to sample size, with 64 subjects in each of the two study groups, it will be possible to detect an effect size of 0.5 standard deviations in a quantitative outcome (a medium effect size in Cohen’s terminology) with 80% power and 2-sided 5% significance level.

VII. Funding

4. Check all types of funding sources for this study.

 Federal Grant/Contract  State, Local Government  International	 Private  Internal Grant Program  Departmental
--	--

 Industry	 Other:
2. Name of Funding Source (e.g. NIH)	NIH/National Library of Medicine
3. Grant/Contract Title*	A Community Health Worker Intervention to Identify and Decrease Barriers to COVID-19 Testing and Vaccination among Los Angeles County Department of Health Safety-Net Patients (Title of the Supplement to parent R01)
4. Grant/Contract #	We are submitting the IRB application as part of the Just in Time for NOT-OD-20-119 (NOSI: Emergency Competitive Revisions for Social, Ethical, and Behavioral Implications (SEBI) Research on COVID-19 testing among Underserved and/or Vulnerable Populations
5. PI of Grant/Contract	[name] (parent RO1), [name], [name]. This supplement is a Multiple PI (MPI) grant.
6. Funding Status	 Funded  Pending  No Funding
7. Expected Award Period	11/2020 to 11/2022
8. Is the funding received as part of a subcontract with another institution?	 No  Yes, name of institution:
9. Please indicate whether the study under review is being conducted under the auspices of a larger umbrella grant.	 Center grant  Training grant  Program projects/multiple project grant  Not applicable  Other: Supplement to RO1
10. Name of larger umbrella grant (e.g., AXIS, CTSI, RTRN): Supplement to R01 grant, Predicting Diabetic Retinopathy from Risk Factor Data and Digital Retinal Images (Parent Grant PI: [name]) (PA-20-135)	

VIII. Statement of Financial Interest or Commitment

1. Does the Principal Investigator or any personnel on this project or their spouses/domestic partners, or dependent children have any significant financial interests related to this research?
 No  Yes (attach Form 133 Financial Disclosure Form)
2. Does the Principal Investigator or any personnel on this project or their spouses/domestic partners, or dependent children have any significant financial interest or commitment with any company, entity, or government agency that sponsors this research?
 No  Yes (attach Form 133 Financial Disclosure Form)

IX. Ancillary Approvals

- | | |
|---|--|
| IX. Ancillary Approvals | |
| 1. Identify the entity that provided scientific or scholarly review for this project. | |
| a. Name of reviewer/review committee: NIH/NLM | |
| b. Date of review or approval: 11-18-2020 | |
| 2. Will you be requesting services from CDU Clinical and Translational Research Center (CTRC)? | |
|  No |  Yes. Please contact CTRC for their services at [contact]. |
| 3. Will you collect biological specimens from participants (e.g., blood, tissue, urine, body fluids, etc.)? | |
|  No |  Yes. Date application submitted to Institutional Biosafety Committee (IBC): |
| | or IBC approval period: (please attach approval notice) |
| 4. Will you be using radioactive material or radio-emitting equipment? | |
|  No |  Yes. Date application submitted to Radiation Safety Committee (RSC)/Radioactive Drug Research Committee (RDRC): |
| | or RSC/RDRC approval period: (please attach approval notice) |

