
4. Study Population: Describe the characteristics of the participant population including, anticipated number, age range, gender, ethnic background and health status. Provide a candid discussion of potential problems related to the study population. Explain the rationale for the use of special classes such as fetuses, pregnant women, children, prisoners, or other vulnerable populations. If women, minorities or children are excluded, provide written justification.

a. Anticipated number of participants to be enrolled:
 
Aim 3: We will recruit a total of 142 patients to allow for approximately 10% attrition from each group. The final number of enrollees we require to successfully complete the study is 128 LACDHS patients composed of 32 African American and 96 Latinx patients who have not completed COVID-19 testing and/or vaccination, according to LACHDS records.
 
Each arm will have at least 64 LACDHS patients, comprised of at least 16 African American and 48 Latinx patients who have not completed COVID-19 testing and/or vaccination

b. Age range: 16 years old and older for Aim 3

c. Gender: all genders for Aim 3

d. Racial/ethnic background: African American and Latinx for Aim 3

e. Describe health status: LACDHS patients who did not complete a lab order for COVID-19 testing or COVID-19 vaccination from Aims 1 and 2

f. Foreign language translation and interpreter required? None

g. Other population characteristics: None

h. Potential problems related to study population: None

i. Vulnerable populations included in the study and the rationale: None

j. If excluding women, minorities, and children, please provide justification:
 
We will exclude children (those under the ages of 16) from this study.
 
Moreover, we are excluding patients under the age of 16 because a) they were not yet eligible for COVID-19 vaccination as of April 19, 2021 and b) decision making on COVID-19 testing and vaccination for children is usually made by their adult caregivers.

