
5. Inclusion/Exclusion Criteria: Indicate the criteria for exclusion and inclusion and explain the system for equitable selection of participants.
 
Aim 3
 
Inclusion Criteria:
 
 • Age 16 years and older • Self-identify as African American or Latinx • English Speaking • Receives primary or specialty care treatment at an LACDHS facility • Has either not completed lab orders for COVID-19 testing and/or vaccination at an LACDHS facility • Have reliable internet access 
Exclusion criteria:
 
 • Not meeting the inclusion criteria listed above

6. Eligibility: How and by whom will it be determined that interested individuals meet the inclusion and exclusion criteria?

Our community partner and Multiple PI (MPI) [name], along with the LACDHS Vaccine Hesitancy Outreach Group, will generate a list of LACDHS patients who have been offered but not taken up the opportunity to get the COVID-19 test and/or vaccine, and who meet other inclusion/exclusion criteria from LACDHS ORCHID. This list will include names of patients and contact information such as phone number, email, address, etc. which study staff will use to ensure that selected patients meet our inclusion criteria by a) cross referencing our data list from Aim 1 to ensure they are LACDHS empaneled patients, b) checking each potential candidate’s medical record to see if they meet the inclusion criteria, and c) calling each potential candidate by telephone to confirm eligibility for inclusion before presenting the opportunity for participation in the study.

7. Participant Identification and Recruitment: Describe the methods used to identify and recruit potential participants. This section should include how, where, when, and by whom the potential participant is approached. Attach a copy of all planned scripts, advertisements, flyers and letters, etc. to the potential participants.

Table 1 below gives our recruitment goals for Aim 3 with a breakdown of the number of participants that will be assigned to the case and control arm:

Table 1.

	Patients not vaccinated	Patients who did not complete lab orders for COVID test	Total
Control	32	32	64
Intervention	32	32	64
		Total Study Participants	128

Identification Strategy

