We will need to enroll at minimum total of 128 participants to successfully complete the study, with a breakdown of 32 African American and 96 Latinx patients to reflect the LACDHS patient population in our study.

Our community partner and Multiple PI (MPI) [name], along with the LACDHS Vaccine Hesitancy Outreach Group, will generate a list of LACDHS patients who have been offered an appointment to be vaccinated and who have not taken the COVID-19 test and/or vaccine, and who meet all other inclusion criteria. The patient list from the DHS Vaccine Hesitancy Outreach Group, is a filtered list of the empaneled patients we obtained from Aim 1. The patient list provided by the DHS Vaccine Hesitancy Outreach Group a list of current patients from DHS County records showing which patients who do not have a completed vaccination status on their record.

Our study staff ([name], project coordinator and [name], research assistant), will work with the support of our two consultant-specialist LACDHS CHWs, who will provide additional insight on recruitment strategies.

For our recruitment process: The two CHW specialists and the intervention CHWs will help us identify and recruit participants by assisting in circulating the patient recruitment flyer within their CHW networks and DHS facilities. By using the CHW’s existing CHW and DHS network, it can assist with quick identification and recruitment of vaccine-hesitant patients. CHWs who work with these identified vaccine-hesitant patients can talk to the patients about the study and validate our research project is a legitimate study to overcome any initial patient skepticism.

The study team will work with the Intervention CHWs and CHW specialists, and follow a standardized referral process. By having a standardized referral process with the CHW network, CHWs can assist with a soft hand off for patients that are interested in learning more about the study. Using CHWs in the referral process can also assist the study team, where the

CHWs can measure and assess the patients' interest in wanting to join the study and help with patient retention.

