We will utilize a randomized control design consisting of one treatment arm and a control arm. African American and Latinx patients who did not complete COVID-19 testing or vaccination will be recruited from the patient list obtained from Aim 1 data pull of the LACDHS EHR. The patient list obtained by the data pull will be filtered by the patient list provided by the LACDHS Vaccine Hesitancy Outreach Group. Based on the inclusion criteria, we will recruit a total of 142 patients to allow for approximately 10% attrition from each group. Patients who meet the inclusion criteria and agree to participate in the 2-month intervention will be randomly assigned to either the intervention or control arm.

We will stratify the randomization on the basis of race/ethnicity and we will use permuted blocks (**see table 3**). We will use a scheme such as found at randomization.com. Here we will define a block size of 4 subjects and determine a random permutation of 2 treatment and 2 control assignments employed the scheme in question. This is repeated to cover the request number of blocks in each stratum in order to randomize the total number of required subjects. We expect our study sample to reflect LACDHS patient population race/ethnicity stratification (9% African American and 68% Latinx).

Table 3 - Stratified Random Sampling

Block	Category	Number of participants to enroll
Block 1	African American + control	18
Block 2	African American + case	18
Block 3	Latinx + control	53
Block 4	Latinx + case	53

We will refer the control arm as “Group 1” and the intervention arm as “Group 2” for the purposes of explaining to prospective participants they will be randomly assigned to a group without compromising the integrity of the study.

Participants will need to complete the consenting process, complete a basic demographic survey, and wait to be randomly assigned to either Group 1 or 2. Once assigned to a group, the study staff will notify the participant of which group they were assigned to. The methodologies of

each respective group are detailed below after the participants are notified which group they were randomly assigned to.

Control Arm- Standard Treatment (Group 1):

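### Table 1 and the Identification Strategy give the post-attrition figure of 128 as the number to assign and enrol, where the rest of the protocol enrols 142

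*Protocol*

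**What the plan says.** **Places that enrol 142**
- Item 4(a), Study Population: "We will recruit a total of 142 patients to allow for approximately 10% attrition from each group". It then gives 128 (32 African American, 96 Latinx) as the final number required to complete the study, with at least 64 per arm.
- Item 8, Intervention Design, repeats the 142 and the attrition allowance. Its Table 3, whose number column is headed as participants to enrol, lists 18 and 18 African American and 53 and 53 Latinx participants.
- Item 17, Payment for Participation, provides for 71 participants in each arm.

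**Places that enrol or assign 128**
- Item 7, Table 1, is introduced as the recruitment goals, broken down by the "number of participants that will be assigned to the case and control arm". It shows 64 control and 64 intervention, 128 in total. Each arm is split 32 and 32 between unvaccinated patients and patients with an uncompleted COVID test order.
- Item 7, Identification Strategy: "We will need to enroll at minimum total of 128 participants to successfully complete the study", again with 32 African American and 96 Latinx patients. Neither place mentions attrition.

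**Power statement**
- Item 25, Data Analysis: "with 64 subjects in each of the two study groups, it will be possible to detect an effect size of 0.5 standard deviations". The calculation is for a continuous outcome, at 80% power and a two-sided 5% level.

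**The concern.** Tables 1 and 3 give different counts for the same event. Under the Intervention Design, participants are assigned after consent and the demographic survey and before any follow-up, so a number assigned is a count before attrition. It cannot be 128 in one table and 142 in the other. The Identification Strategy has the same problem with the number to enrol: 128 enrolled would satisfy its sentence, yet would not be expected to give the 128 completers that item 4(a) requires.

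Item 7 is where the protocol states its recruitment goals, and neither its goals table nor its enrolment sentence gives 142. A reader working from that item alone could regard recruitment as finished with no allowance for the attrition that the plan expects. At stake are the 64 completers per arm behind the power statement.

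**Working it through.** **Inputs**
- Effect size 0.5 SD, two-sided 5% level, 80% power, 64 per arm: item 25.
- Test: item 25 states "Bivariate analyses will include independent t-tests models" for trust and self-efficacy, so a two-sample t-test is used.
- Allocation 1:1: item 8 (blocks of 4, two assignments to each arm).
- Attrition about 10% in each group, 142 recruited, 128 required to complete: item 4(a).

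**Step 1. Reproduce the plan's own power.** With n per arm, the noncentrality is 0.5 × √(n/2) on 2n − 2 degrees of freedom.
- n = 64: 0.5 × √32 = 2.83, power 80.1% (normal approximation 80.7%).
- The smallest n for 80% is 63.8, so 64 per arm.

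The stated 80% reproduces.

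**Step 2. Reproduce the attrition allowance.** 128 / 0.9 = 142.2, against the stated 142. In the other direction, 142 × 0.9 = 127.8, or 63.9 per arm, with power 80.1%. Strict rounding up would give 143, but the attrition rate is itself approximate and the difference is immaterial.

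**Step 3. Which figure is before attrition?**
- Table 3: 18 + 18 + 53 + 53 = 142.
- Per arm: 18 + 53 = 71, which matches the payment section.
- African American: 18 + 18 = 36, and 36 × 0.9 = 32.4.
- Latinx: 53 + 53 = 106, and 106 × 0.9 = 95.4.

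The 32 and 96 in the Identification Strategy are therefore the Table 3 strata after attrition. The 36/106 against 32/96 difference is the 142 against 128 difference split by race/ethnicity, not a second error.

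**Step 4. What follows if recruitment closed at 128?** 128 × 0.9 = 115.2 completers, or 57.6 per arm.

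| Enrolled | Completers per arm | Power, t-test | Power, normal approximation | Effect detectable at 80% power (t-test) |
|---|---|---|---|---|
| 142 | 63.9 | 80.1% | 80.7% | 0.50 SD |
| 128 | 57.6 | 75.8% | 76.5% | 0.53 SD |

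As in the protocol's own calculation, these figures ignore covariate adjustment, grouping of intervention participants under a CHW, and multiple imputation.

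**The case against.** The strongest case for leaving the text alone has three parts.

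1. The Identification Strategy sentence sets a floor, not a target. Enrolling 142 satisfies it, and its closing words echo item 4(a), where 128 is clearly the number that must complete. This stands for that sentence. It does not cover Table 1, which has no wording about a minimum and describes its numbers as those assigned.

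2. Nothing in the protocol stops recruitment at 128. Item 7 itself plans outreach beyond that: at least 600 people by mail and telephone, of whom a third answer and half of those agree (600 × 1/3 × 1/2 = 100), and at least 600 by text message with 75 expected to enrol, besides CHW referral. The two lists may overlap, so 100 + 75 = 175 is an upper reading. This also stands. A reader might infer that the trial is planned at 128 and is underpowered at 76%. The documents do not support that inference, because 142 appears in the population, design and payment items.

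3. The 76% assumes an analysis of completers only, whereas item 25 plans multiple imputation when 10% or more of the data are missing, and also covariate-adjusted models. This is fair as a caution: 76% is a scenario figure. Imputation does not generally restore the information lost with missing post-survey outcomes, however, and the power statement makes no allowance for it.

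**Conclusion.** The inconsistency is real and worth correcting. Table 1 presents the post-attrition number as the number assigned, and the Identification Strategy presents it as the minimum to enrol, against 142 everywhere else that enrolment is counted. The document itself shows which figure is misplaced, so no new assumption is needed to resolve it.

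It is a labelling error, not an underpowered design: 142 enrolled gives about 128 completers and about 80% power. The loss to about 115 completers and about 76% power, roughly 4 percentage points, arises only if recruitment is closed at the item 7 figure, attrition is the assumed 10%, and the comparison is a t-test on completers. Whether staff would use item 7 to decide when to stop is a possibility, not something the protocol states.

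**What to change.** **Table 1.** Either of two repairs works:
- Keep the numbers and relabel the table as expected completers per arm. This is the simpler change.
- Restate it as 71 control + 71 intervention = 142 assigned. The two column cells must then be restated so that they sum. An odd 71 cannot be split equally, so changing only the totals would leave 32 + 32 against 71.

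**Identification Strategy.** Say that 142 participants (36 African American, 106 Latinx) will be enrolled and randomised so that about 128 (32 and 96) are expected to complete the post-survey. Use 128 elsewhere only as the number of completers.

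**Cost.** One table and one sentence. No participants or payments beyond the 142 already planned.

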CHW's can confirm if patients they work with are not vaccinated. CHW-identified patients will most likely be in the vaccine hesitant list provided by the LACDHS Vaccine Hesitancy Outreach Group, as their records are obtained from ORCHID and updates from California Immunization Registry System (CAIRS). After streamlining the referral process, the study team will cross reference the referred patient with the patient list provided by the LACDHS Vaccine Hesitancy Outreach Group and the patient list from Aim 1. This will work in tandem with the process we have identified with the vaccine outreach group list because the CHWs that work with them will be able to do a soft hand off. The hand off will provide a stronger connection between the patient and the study, and will validate the project simultaneously.

In addition to using CHWs as the preferred source of identification and recruitment of patients for the study, we will have an additional process of recruiting patients by virtual communication methods such as phone calls, texts, and emails. Using the list of vaccine-hesitant patients from the LACDHS Vaccine Hesitancy Outreach Group, the study staff will filter the list of LACDHS patients to ensure only include patients who meet the inclusion criteria (16 years and older, self-identify as Latinx or African American) are on the list.

Preferred method:

- CHW network will assist in identifying vaccine-hesitant and non-vaccinated people they work with at LACDHS facilities
- CHWs will talk to patients they work with about the study and provide them a flyer in case they are interested in participating. If a patient expresses they are interested in the study, the CHW will notify the study team with the patient's contact information.
- Study team will cross reference the lists of vaccine-hesitant patients provided by LACDHS Vaccine Hesitancy Outreach Group and Aim 1 data pull.
- If the patient is in the list, the study team can follow up with the referred patient to talk to them about the study and provide them additional details about the study.
- If the patient is interested in participating in the study, the study team will send them the consent forms and continue with study enrollment process.

Recruitment Strategy - telephone script

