8. Methodology and Procedures: Describe the research procedures that will be followed. Please indicate those that are experimental and those that may be considered to be standard treatment. Describe all activities involving research participants and explain the frequency and duration of each activity.

Recruitment of CHWs:

Currently, there are 76 CHWs working across the LACDHS health system and officially they are allowed to work 24 hours/week outside of their allotted weekly County work hours. Using our MPI's and CHW networks, we will recruit 3 African American and 9 Latinx CHWs from the pool of currently employed LACDHS CHWs to participate and provide the intervention in this study. We estimate that each CHW will spend 24 hours over 2 weeks for the enhancement training pre-intervention, 6 hours/week for group classes with patients and 10 -14 hours/week for personalized patient encounters over the two months of intervention implementation.

Training of CHWs:

We developed a training curriculum for the Intervention CHWs on how to implement the patient modules that address COVID-19 testing, vaccination, and care overall. The patient modules are based on our preliminary findings from Aims 1 and 2.

Leveraging the resources of the CDU CHW Academy, study staff will train the Intervention CHWs virtually via Zoom. The training will take about 24 hours and will be delivered over the course of a month, allowing flexibility to CHW participants. Intervention CHWs will receive CITI training to ensure that they are compliant with IRB protocols and be IRB approved.

Table 2 provides the training outline of how some barriers will be addressed systematically in the CHW training, in terms of the content of the curricular modules and the learning objectives. We developed the training curricula and with input from our two CHW specialists, they provided their assessments in tandem with the implementation and analysis of Aims 1 and 2.

Table 2: CHW Training Plan			
Identified Barriers to COVID-19 testing and vaccinations from Aims 1+2	How CHW Training Addresses Barriers	Curriculum Content	Learning Objectives
Barrier #1 Patient Mistrust of	Demonstrate ways of building trust virtually with patients based on their shared identities,	Building Trust in Virtual Communication Settings/ Historical Mistrust and	1. Explain why trust is important in the patient relationship 2. Review and apply the steps for

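### Intervention CHWs may refer their own patients, who are then individually randomised; controls linked to a trained CHW may be informally exposed, and the plan neither prevents nor records it

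*Protocol*

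**What the plan says.** **Who recruits.** Protocol VI.7 (Participant Identification and Recruitment) states that "The two CHW specialists and the intervention CHWs will help us identify and recruit participants by assisting in circulating the patient recruitment flyer" through their networks and the health system's facilities. It also places the intervention CHWs in the standardised referral process.

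**From whom.** The same section says "CHWs who work with these identified vaccine-hesitant patients can talk to the patients about the study and validate our research project". Under the preferred method, "CHWs will talk to patients they work with about the study and provide them a flyer in case they are interested in participating". Mail with a follow-up call, text messages and facility flyers are further routes that need no CHW.

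**Who the intervention CHWs are.** VI.8 (Recruitment of CHWs) says "we will recruit 3 African American and 9 Latinx CHWs from the pool of currently employed LACDHS CHWs", out of 76. Their study hours come on top of their County hours. They receive about 24 hours of training before the intervention, covering trust, COVID-19 information, social support and technology (Table 2).

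**Allocation.** VI.8 (Intervention Design) randomises individual patients, stratified by race/ethnicity, in blocks of four made up of a "random permutation of 2 treatment and 2 control assignments". Referral source and usual CHW play no part.

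**The arms.** Classes and personal sessions go to patients randomised to the intervention arm. The control arm is described as a monthly reminder call from the outreach group, plus surveys six weeks apart.

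**Sample size.** VI.25 (Data Analysis) claims that "with 64 subjects in each of the two study groups" the trial can detect an "effect size of 0.5 standard deviations in a quantitative outcome" "with 80% power and 2-sided 5% significance level".

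**The concern.** Allocation is by patient, but what the intervention adds lies partly in the CHW: trained skills in building trust and answering COVID-19 questions. If an intervention CHW refers a patient from the usual caseload, 1:1 randomisation sends that patient to control about half the time. The CHW keeps the County job and has been trained before delivery starts, and intervention start dates are staggered with recruitment. Ordinary contact during the control patient's six weeks could therefore carry some of the same content.

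Trust, self-efficacy and intent are the three key measures, and they are what such contact would shift. If it works in the same direction as the programme, the estimated difference shrinks. The plan does not restrict which CHW may refer, screen for a link or record CHW contact among controls. Afterwards nobody could say whether dilution occurred or how much. The sample size has no margin for it.

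**Working it through.** **1. Reproduce the plan's figure.** Inputs from VI.25: 64 per arm, effect 0.5 SD, two-sided 5%. The two-sample t-test gives power 80.1%, and the exact requirement for 80% is 63.8, so 64 per arm. The stated 80% is correct and assumes no dilution.

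**2. Trace the path to exposure.**
- Intervention CHWs circulate flyers and take part in referral: stated in VI.7.
- CHWs refer patients they work with, as the preferred route: stated in VI.7 for CHWs generally. That intervention CHWs refer their own patients is permitted, not separately stated.
- Patients are randomised individually without regard to CHW: stated in VI.8.
- Intervention CHWs continue in County work: follows from VI.8, where study hours are outside County hours.
- A control patient sees a trained CHW during follow-up: inferred, not stated.

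**3. Dilution model.** Let f be the share of controls whose usual CHW is an intervention CHW, and s the fraction of the full effect passed on informally. Expected contrast = 0.5 × (1 − f × s). Neither f nor s is in the protocol.

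**4. A range for f.** If every control had a CHW and links were proportional, f = 12/76 = 15.8%. If half the controls came by routes with no CHW link (an assumption), f = 0.5 × 15.8% = 7.9%.

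The protocol's own yields make the lower figure plausible. Mail and phone: 600 × 1/3 × 1/2 = 100. Text: 600 × 1/4 × 1/2 = 75. Together 175, against the 142 to be recruited, though the two sets of 600 may overlap. On the other side, naming the intervention CHWs as recruiters could push f above the proportional value.

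**5. Results with 64 per arm (t-test), s assumed at 25% to 50%.**

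| f | s | f × s | Contrast (SD) | Power | n per arm for 80% |
|---|---|---|---|---|---|
| 0 | – | 0 | 0.500 | 80.1% | 64 |
| 7.9% | 25% | 0.020 | 0.490 | 78.6% | 67 |
| 7.9% | 50% | 0.039 | 0.480 | 76.9% | 70 |
| 15.8% | 25% | 0.039 | 0.480 | 76.9% | 70 |
| 15.8% | 50% | 0.079 | 0.461 | 73.4% | 75 |

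Over this range the loss is 0.01 to 0.04 SD and about 1.5 to 7 percentage points of power.

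**The case against.** The strongest reply is that the programme is structured and confined to one arm: six classes of up to two hours and six personal sessions of up to one hour, delivered by CHWs assigned to intervention patients. No passage has a control patient seeing an intervention CHW during follow-up or receiving curriculum content in routine care. The flyer task given to intervention CHWs concerns networks and facilities. The wording about patients they work with refers to CHWs in general. This stands, and it limits the point to a risk.

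Two stronger readings are tempting, and neither is supported. One is that the control arm receives part of the intervention. The documents show only that some controls could be exposed, and only those linked to one of 12 CHWs. The other is a severe loss of power. With half the controls linked and half the effect passed on, the contrast would be 0.5 × (1 − 0.25) = 0.375 SD and power about 56%. Nothing supports 50% linkage, which is about three times the proportional figure, and the routes that need no CHW point lower.

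The protocol also gives reasons for CHW-led recruitment: overcoming scepticism and helping retention. Aim 3 is described as a pre-test, and dilution of this kind would not create a false positive. These are fair reasons to keep CHWs in recruitment. They do not require the 12 who deliver the intervention to be among the recruiters, since the two specialists and the rest of the network can do the same work.

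**Conclusion.** The point holds as an unguarded risk of contamination. Intervention CHWs may refer their own patients, allocation ignores that link, and the plan has no means to prevent or detect informal exposure of linked controls. The likely direction is toward no difference.

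Its size cannot be derived from the protocol. Under the assumed ranges (about 8% to 16% of controls linked, 25% to 50% of the effect passed on), the planned 0.5 SD contrast falls to about 0.49 to 0.46 SD, and power falls from 80% to between about 79% and 73%. A reader might infer that a null result would be uninterpretable. A loss of at most 0.04 SD within this range does not support that. What can be said is that, with no record of CHW contact, the dilution could be neither measured nor ruled out. The change is worth making because the safeguard is cheap.

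**What to change.** 1. In VI.7, exclude the 12 intervention CHWs from referral and recruitment. Keep the two CHW specialists, the other CHWs, the outreach group's list, mail, text and facility flyers.
2. On the existing eligibility call, before randomisation, ask whether an intervention CHW is the candidate's usual CHW. Do not enrol those who say yes.
3. If that exclusion is unacceptable, at minimum record the answer, record usual-CHW contact in both arms during follow-up, and pre-specify a sensitivity analysis without linked patients. Define the link by the answer given before randomisation and drop linked patients from both arms, so that the comparison remains a randomised one.

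**Cost.** At most 12 of 76 CHWs are lost as referral sources, so recruitment may be slightly slower. There is one added screening question and one narrow exclusion, which trims the eligible population a little. Intervention CHWs are the CHWs for whom VI.8 states research-ethics training, so more of the referral falls to CHWs for whom none is stated. The plan already uses that wider network for referral, so this cost is small. No larger sample is needed if linked patients are not enrolled.
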